### 9.2 Primary study parameter(s)

The primary outcome parameter of this study is the completeness of hourly urine production registration. It refers to the extent to which the two devices, the manual urine monitor and the FlowSure device, accurately capture and record hourly urine production data over a 24-hour period.

Completeness of hourly urine production registration represents the proportion or percentage of the total hourly measurements that are successfully recorded by each device.

For example, if a patient's urine output is measured every hour for 24 hours, the completeness rate indicates how many of these hourly measurements are successfully captured by the device.

In this study, the primary objective is to compare the completeness of hourly urine production registration between the manual urine monitor and the FlowSure device as registered in the electronic health record. The manual urine monitor has an assumed completeness rate of approximately 50% of hourly registrations, while Device B (FlowSure) is expected to have a higher completeness rate of over 90%.

By assessing the primary outcome parameter, the study aims to determine whether the FlowSure device significantly improves the completeness of hourly urine production registration, as compared to the manual urine monitor. The primary outcome will provide crucial insights into the devices' ability to accurately capture and register hourly urine production data, which is vital for monitoring and managing various clinical conditions.

The completeness of hourly urine production registration serves as a key indicator of the devices' reliability, usability, and potential clinical utility and safety. The primary outcome parameter will be analysed statistically, as described earlier, to assess the significance of the observed difference in completeness rates between the two devices.

## 10. ETHICAL CONSIDERATIONS

### 10.1 Regulation statement

The study will be conducted in adherence to the principles outlined in the Declaration of Helsinki, which is a set of ethical guidelines for medical research involving human subjects. The most recent version of the Declaration of Helsinki can be found at [www.wma.net](http://www.wma.net). Furthermore, the study will be conducted in accordance with the requirements of the Medical Research Involving Human Subjects Act (WMO) and other relevant guidelines, regulations, and acts governing clinical research. These include but are not limited to local and international regulations pertaining to the protection of human subjects, informed consent, confidentiality, data protection, and ethical considerations. The study protocol and procedures have undergone appropriate ethical review and approval by the relevant institutional review board or ethics committee. Stringent measures will be implemented to ensure the rights, safety, and well-being of the study participants throughout the trial.

### 10.2 Recruitment and consent

In this clinical study, hospitalized patients with a catheter will be recruited as potential participants. The medical team and research staff will collaborate to identify eligible patients who meet the study's requirements, specifically the inclusion and exclusion criteria. Upon identifying potential participants, the research team will approach them to explain the study's purpose, procedures, potential risks, benefits, and expected outcomes. The initial contact and referral to the research team will be made by the medical team responsible for the patient. The researchers will provide detailed information about the study in a clear and understandable manner, ensuring that all aspects of the study are comprehensively conveyed. Patients will be given ample time to ask questions and seek clarification.

In accordance with ethical guidelines and regulations, the research team will emphasize that participation in the study is voluntary and that patients have the right to decline participation or withdraw at any time without any negative consequences for their medical care.

The informed consent process will be conducted in a private and confidential setting to protect the participants' privacy and ensure a conducive environment for discussion.

Patients who express an interest in participating and meet the eligibility criteria will be provided with a written informed consent form. The research team will thoroughly explain the contents of the consent form, including the study's objectives, procedures, potential risks and benefits, confidentiality measures, and contact information for any questions or concerns. Patients will be encouraged to take their time to review the informed consent form and ask further questions before making a decision. If patients voluntarily decide to participate, they will be asked to sign the informed consent form, indicating their willingness to take part in the study. The research team will emphasize that signing the form does not waive any of their rights and that they can withdraw from the study at any point without penalty. The informed consent process will prioritize patient autonomy, respect for their decision-making capacity, and the protection of their rights and welfare. The research team will ensure that patients fully understand the nature of the study, the potential benefits and risks involved, and their rights as participants.

### **10.3 Benefits and risks assessment, group relatedness**

In this clinical study, a comprehensive assessment of benefits and risks will be conducted to evaluate the potential impact of the research on participating patients. The benefits of the study include the opportunity to contribute to medical knowledge, potentially improving the care for hospitalized patients with a urine catheter. By participating, patients may indirectly benefit from the advancements in medical care that result from the study's findings.

The potential risks associated with the study are minimal. In case the automated FlowSure device does not register correct, urine production can always be checked by reading the changes from the urine collection bag. The research team will take appropriate measures to minimize risks by monitoring patients closely for any potential complications.

Throughout the study, the benefits and risks will be continuously evaluated and monitored to ensure the well-being and safety of the participants. Any unexpected adverse events or significant findings will be promptly addressed, and appropriate actions will be taken to mitigate risks and protect the participants' welfare.

**10.4 Compensation for injury**

The IRB has granted dispensation from the statutory obligation to provide insurance, because participating in the study is without risks. The sponsor has a liability insurance which is in accordance with article 7 of the WMO

**10.5 Incentives**

No incentives or compensation for participants will be used for the study.

## 11. ADMINISTRATIVE ASPECTS, MONITORING AND PUBLICATION

### 11.1 Handling, storage and exchange of data and documents

All collected data will be securely stored and accessible only to authorized personnel involved in the study. Participant information will be anonymized and coded to maintain confidentiality, with any identifying details kept separate from the research data. Electronic data will be stored on password-protected servers, with regular backups and appropriate security measures in place to prevent unauthorized access. Physical documents will be stored in locked cabinets or rooms, accessible only to authorized personnel. The research team will strictly adhere to data protection laws and regulations, ensuring that all necessary approvals and permissions for data storage and handling are obtained (EU General Data Protection Regulation and the Dutch Act on Implementation of the General Data Protection Regulation. (in Dutch: Uitvoeringswet AVG, UAVG). Data and documents will be retained for the required duration as per regulatory guidelines (, and their disposal at the end of the study will be conducted in a secure and confidential manner.

Data sharing and exchange will be done using coded participant information. Commercial party or parties that will bring the urinometer to the market will be given access to encoded data in order to obtain (inter)national certification for healthcare use. This involves sharing data with certifying organizations such as a European Notified Body, the U.S. Food and Drug Administration, and foreign (government) institutions involved in approving the device for the local foreign market.

### 11.2 Monitoring and Quality Assurance

For the study, no formal study monitoring and quality assurance activities will be conducted due to several factors. Firstly, the study involves a low-risk intervention Secondly, the study is of limited duration and involves a relatively small sample size, making it logistically challenging and resource-intensive to implement formal monitoring and quality assurance measures. However, the research team will ensure strict adherence to the study protocol, good clinical practice guidelines, and relevant ethical standards to maintain the integrity of the data and protect the rights and safety of the participants. Regular communication and collaboration among the study team members will facilitate ongoing review and assessment of the study progress, thereby addressing any issues or concerns that may arise during the course of the research.

### **11.3 Amendments**

All amendments will be notified to the METC that gave a favourable opinion.

A 'substantial amendment' is defined as an amendment to the terms of the METC application, or to the protocol or any other supporting documentation, that is likely to affect to a significant degree:

- the safety or physical or mental integrity of the subjects of the trial
- the scientific value of the trial
- the conduct or management of the trial; or
- the quality or safety of any intervention used in the trial.

All substantial amendments will be notified to the METC and to the competent authority.

Non-substantial amendments will not be notified to the accredited METC and the competent authority but will be recorded and filed by the sponsor.

### **11.4 Annual progress report**

The sponsor/investigator will submit a summary of the progress of the trial to the accredited METC once a year. Information will be provided on the date of inclusion of the first subject, numbers of subjects included and numbers of subjects that have completed the trial, serious adverse events/ serious adverse reactions, other problems, and amendments.

### **11.5 Temporary halt and (prematurely) end of study report**

The sponsor will notify the accredited METC and the competent authority of the end of the study within a period of 90 days. The end of the study is defined as the last patient's last visit. The sponsor will notify the METC immediately of a temporary halt of the study, including the reason of such an action. In case the study is ended prematurely, the sponsor will notify the accredited METC and the competent authority within 15 days, including the reasons for the premature termination. Within one year after the end of the study, the investigator/sponsor will submit a final study report with the results of the study, including any publications/abstracts of the study, to the accredited METC and the Competent Authority.

### **11.6 Public disclosure and publication policy**

Data from the study will be publicly disclosed through presentations at a scientific conference and through publications in peer-reviewed journals.

## STRUCTURED RISK ANALYSIS

### 11.7 Potential issues of concern

#### a. Level of knowledge about the device's technology.

The mechanism of action of the investigational FlowSure device is known and straightforward. The investigational FlowSure device measures weight and translates weight to hourly urine production. The underlying assumption is that the molecular weight of urine is similar to water (in fact 1.007) and therefore close enough to translate grams of urine to diuresis in millilitres.

#### b. Previous clinical experience with manual urine monitors:

There is extensive experience with the use of manual urine monitors in clinical care.

#### c. Potential for device-related injuries or harm:

There is no risk of device-related injury since the device does not touch the patient. Electrical safety and electromagnetic compatibility are secured as part of the local Convenant-Medisch-Technologie-authorization-procedure.

The investigational device demonstrates compliance with the internationally recognized ISO standard, specifically the IEC 60601-1, ensuring its compatibility and adherence to established industry requirements. FlowSure is housed in an IP67 certified housing from Fibox and is powered by a medical power supply. This enters the housing by means of a low voltage connector IP65 sealed by a screw socket. The on/off switch is IP65.

#### d. Compatibility with patient population:

The device will be used only in patients who already have, for medical considerations not related to the study, a urine catheter inserted.

#### e. Accuracy and reliability of device measurements:

Evaluating the accuracy and reliability of the device's measurements is paramount. In Part A of the study the investigation automated urine monitor FlowSure will be used in conjunction with standard manual urine production monitor. Patients will therefore be double monitored in Part A.

The protocol will transition to part B only when the investigational FlowSure device performance is within 15% difference from manual monitoring. In Part B of the study the investigational FlowSure device will replace the manual monitor. The nurse will be able to read the urine production manually from the urine collection bag (without the measuring chamber) as the bag is transparent with an approximate graduation scale.

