## SUMMARY

**Rationale:** Current manual diuresis monitoring is labour intensive, to optimally monitor hospitalised patients with a urine catheter. The automated FlowSure monitor aims to automate diuresis monitoring and data processing to the electronic medical record.

**Objective:** The primary endpoint is the *accuracy* of urine production monitoring using the automated FlowSure monitoring compared to the standard manual method of monitoring.

**Study design:** Part A is single arm intervention study in which patients will receive *both* the manual monitors and automated FlowSure monitor (both devices will be used in conjunction).

Part B is a two-arm randomized non-blinded intervention study in which patients will be monitored with *either* the manual monitoring or automated FlowSure monitor.

**Study population:** Patients admitted to the hospital who ~~-~~ for medical reasons unrelated to the study have a urine catheter inserted.

**Intervention (if applicable):** in part A patient will undergo double urine monitoring as they receive both the manual urine monitor and automated FlowSure monitor.

In part B patients will be randomized to monitoring with the manual monitor or to automated monitoring with the automated FlowSure monitor.

**Main study parameters/endpoints:** The primary outcome event in Part A will be the *accuracy* of urine measurement over two set time intervals (a nursing shift of 8 hours and a full 24-hour period) using manual monitoring and automated monitoring.

The measurements of both the manual and the automated urinemonitor will compared against the golden standard: the total urine production measured in a measuring cup by draining the collection bag.

The primary outcome in part B of the study will accuracy of measurement over a set time interval (a nursing shift of 8 hours and a full 24-hour period) using manual monitoring *and* automated monitoring. Therefore, the completeness of the hourly diuresis registration will be compared between the manual and automated measurement groups.

**Nature and extent of the burden and risks associated with participation, benefit, and group relatedness:** There is no direct benefit for patients participating in the study. The societal/research benefit of the study lies in the potentially improved diuresis monitoring and registration in the medical record of the patient which will improve the quality, (costs) effectiveness and accuracy of patient monitoring and therefore patient safety.

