### **6.1 Summary of findings from non-clinical studies**

The FlowSure team has conducted a non-human study at the cardiology department of the Amsterdam UMC. In the study we have demonstrated the functionality and accuracy of the device in a mock set-up. In the set-up a Braun infusion pump was used to simulate a patient with diuresis and the investigational FlowSure device was tested for operability, accuracy, and safety. The results demonstrated that the measurement with the FlowSure device is more accurate than the Braun infusion pumps that are currently in use in our hospital.

The infusion pump was set at a fixed rate of 50 millilitres per hour. The golden standard is the manual measurement with a measuring cup. The FlowSure accuracy was within 1% margin from the gold standard, whereas the margin for the infusion pump is up to 10%.

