### **6.3 Summary of known and potential risks and benefits**

There is no direct benefit for patients participating in the study. The societal/research benefit of the study lies in the potentially improved diuresis monitoring and registration in the medical record of the patient which will improve the quality and effectiveness of patient monitoring and therefore patient safety.

Risks: The foreseeable added risks associated with the use of the FlowSure in Part A are negligible as using the automated monitor will be additive to the manual measurements.

In part B patient will be monitored with either a manual monitor or the automated FlowSure monitor. If either monitor fails, the hourly urine production can be estimated by dividing the total urine collection since monitoring started by the hours that have passed since insertion of the urine catheter. The nurse will be able to read the urine production manually from the urine collection bag (without the measuring chamber) as the bag is transparent with an approximate graduation scale.

Risk-benefit analysis: Since the expected clinical-scientific benefit of this study is estimated as large and the clinical investigation is, in the opinion of the investigators, proportional to the

added risk associated with the use of the medical device, which is estimated as low, the overall risk-benefit profile of the study is favourable.

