### 7.1 Study parameters/endpoints

#### 7.1.1 Main study parameter/endpoint

The primary outcome event in Part A will be the accuracy of urine measurement over two set time intervals (a nursing shift of 8 hours and a full 24-hours period) using manual monitoring and automated monitoring. The golden standard is the total urine production measured in a measuring cup by draining the collection bag in comparison with the new FlowSure device. The primary outcome in part B of the study will be the completeness of the hourly diuresis registration will be compared between the manual and automated measurement groups.

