**7.6 Premature termination of the study**

The criteria for prematurely terminating the study includes - but are not limited to the following Safety concerns - insufficient or inappropriate device functioning (e.g. when the device produces erroneous measurements that deviate >20% from the golden standard) or regulatory requirements.

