### **11.8 Synthesis**

Considering the above structured risk analysis, the risk for the study subjects is deemed low as in case of device malfunction the nurse can always revert to manual monitors. This results in an acceptable risk profile.

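### The rule for starting Part B judges FlowSure against manual monitoring, while the Part A endpoint judges both monitors against the measuring cup; one accuracy reference must be named

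*Combined protocol and SAP*

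**What the plan says.** The protocol names a comparator for FlowSure's accuracy in several places, and they differ.

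- **Structured risk analysis, 11.7 e (condition for starting Part B):** "The protocol will transition to part B only when the investigational FlowSure device performance is within 15% difference from manual monitoring". The sentences around it speak of the standard manual monitor used together with FlowSure in Part A and replaced by FlowSure in Part B.
- **Summary, Objective:** accuracy is assessed "using the automated FlowSure monitoring compared to the standard manual method of monitoring".
- **Summary, main endpoints, Part A:** "The measurements of both the manual and the automated urinemonitor will compared against the golden standard". Here the manual monitor is one of the two methods under test.
- **Section 7.1.1:** "The golden standard is the total urine production measured in a measuring cup by draining the collection bag".
- **Section 7.6:** one example of a reason to end the study is "when the device produces erroneous measurements that deviate >20% from the golden standard".
- **Section 1 (Preclinical research) and section 6.1:** the bench study took a measuring-cup reading as gold standard and described that reading as a manual measurement. Section 6.1 reports: "The FlowSure accuracy was within 1% margin from the gold standard".

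No section says how these references relate to each other.

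**The concern.** The 15% condition is the stated check before FlowSure replaces the chamber monitor in half of the Part B patients. If it is measured against the chamber monitor, the yardstick is a method whose own accuracy Part A sets out to test. Any systematic error in that method then passes into the decision. If the chamber monitor and FlowSure err in the same direction, the chamber monitor can make FlowSure look closer to the truth than it is. If they err in opposite directions, it can fail a device that is acceptable against the cup.

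The wording also leaves room for two different decisions from the same Part A data, depending on which comparator the team uses. That choice should not be open once the data have been seen.

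**Working it through.** The plan gives no figure to reproduce here, so the check has two parts: which comparator the text means, and what follows if it is the chamber monitor.

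**1. Which comparator.** Section 11.7 e refers to the manual monitor both before and after the 15% condition, and the Summary treats that monitor and the cup as separate things. The chamber monitor is therefore the natural reading. The bench-study text uses the word manual for a cup reading, so the cup remains possible. The Summary Objective names the standard manual method, which fits the condition as written but not the endpoint text in the same Summary.

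**2. Consequence if the chamber monitor is meant.**

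Inputs from the documents: the 15% limit (11.7 e), the 20% example (7.6), the 1% bench figure (6.1).

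Assumptions: f is FlowSure's proportional error and m the chamber monitor's systematic proportional error, both against the cup. The condition is taken as a ratio of totals with the manual reading as denominator. The documents give no value for m and do not specify the ratio.

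The condition sees (1+f)/(1+m) - 1. It is met when f lies between 0.85(1+m) - 1 and 1.15(1+m) - 1.

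| Assumed m | Lower edge for f | Upper edge for f |
|---|---|---|
| -10% | 0.85 x 0.90 - 1 = -23.5% | 1.15 x 0.90 - 1 = +3.5% |
| -5% | 0.85 x 0.95 - 1 = -19.25% | 1.15 x 0.95 - 1 = +9.25% |
| 0 | -15% | +15% |
| +5% | 0.85 x 1.05 - 1 = -10.75% | 1.15 x 1.05 - 1 = +20.75% |
| +10% | 0.85 x 1.10 - 1 = -6.5% | 1.15 x 1.10 - 1 = +26.5% |

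These are the edges of what could pass, not expected values. At m = 0 the two comparators give the same window. An edge lies beyond 20% only if m is above 1.20/1.15 - 1 = +4.3% or below 0.80/0.85 - 1 = -5.9%.

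Worked cases:

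- f = +18%, m = +5%: 1.18/1.05 - 1 = +12.4%. It passes, although it is outside 15% of the cup.
- f = +18%, m = 0: +18.0%. It fails.
- f = +10%, m = -5%: 1.10/0.95 - 1 = +15.8%. It fails, although it is within 15% of the cup.

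In the plan's favour:

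- An exact device (f = 0) passes for any m from 1/1.15 - 1 = -13.0% to 1/0.85 - 1 = +17.6%.
- Any device with f between -1% and +1% passes for m from 1.01/1.15 - 1 = -12.2% to 0.99/0.85 - 1 = +16.5%.

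With the cup as reference, the window is -15% to +15% whatever m is.

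**The case against.** The strongest reply is that agreement with the method being replaced is a sensible condition for replacing it, and the Summary Objective supports it. FlowSure's own error is addressed separately by the Part A endpoint. This stands as a defence of the comparison being made at all. It does not explain why the method under test should decide the transition when a better reference is already collected, and no section offers that justification.

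Second, the author may simply have meant the cup. That is possible. The shift worked out above would then disappear, leaving a clarification of wording.

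Third, the harmful cases are hypothetical. They need a sizeable FlowSure error together with a manual bias that the documents do not report, and the only documented accuracy figure is the bench result. This also stands, with the limit that the bench test was a mock set-up with a pump at a fixed rate, not clinical use. Random manual error with mean zero would not shift the window like this; it would largely average out in a group mean.

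Fourth, there are backstops. A deviation above 20% from the cup meets the termination example whatever 11.7 e shows, although that is only an example and its use is discretionary. Section 6.3 adds: "If either monitor fails, the hourly urine production can be estimated by dividing the total urine collection since monitoring started by the hours" elapsed since catheter insertion. Section 11.8 says that "in case of device malfunction the nurse can always revert to manual monitors". Both are written for a monitor that fails or malfunctions, so they depend on someone noticing; a steady bias may not be noticed.

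A reader might also infer that the 15% and 20% limits contradict each other. The documents do not support that: one is a condition for progressing, the other an example of a reason to stop, and such limits may differ. Neither says whether it applies per reading, per patient or to a mean.

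**Conclusion.** The inconsistency is in the current text and should be corrected. On the natural reading, the rule for starting Part B uses a comparator that Part A itself tests against the cup. On the other reading, the rule says manual monitoring where it means the cup.

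The size of the consequence is conditional. It rests on the chamber-monitor reading, a ratio of totals, proportional errors and an assumed m. Under those assumptions a 5% manual bias moves the edges of the pass window by roughly 4 to 6 percentage points (for example, from +15% to +20.75%).

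A reader might infer that an inaccurate FlowSure is likely to be let into Part B. The documents do not show that: they report no manual bias and no clinical FlowSure error, and a device performing as on the bench would pass correctly over a wide range of m.

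Two further gaps are separate matters and add nothing to the weight of this point: section 9 describes no Part A accuracy analysis, and section 7.2 does not say when the bag is drained into the cup. Both would exist whichever comparator were used.

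**What to change.** In section 11.7 e, make the measuring-cup total the reference for the condition to start Part B, and keep the sponsor's 15%. Report FlowSure against the manual monitor as supporting information. Reconcile the Summary (Objective and endpoint text), 7.1.1, 7.6 and 11.7 e so that one accuracy reference is named throughout, and avoid the bare word manual wherever the cup is meant. Settle this before Part A data are seen.

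The cost is protocol wording and one simple paired comparison. The cup total is already required by the Part A endpoint, so the comparison needs no new kind of measurement.
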